4 STUDY POPULATION

4.0 Inclusion Criteria

Patients participating in this study must:

1. Have a biopsy-proven diagnosis of metastatic uveal melanoma, previously untreated with anti-PD-1,CTLA-4 and/or LAG-3 blocking antibodies.
2. Agree to undergo a pre-treatment and a post-treatment fresh biopsy of the tumor, if needed, safe and feasible as determined by the investigator.
3. Have completed all previous therapy for a minimum of 3 weeks before the first dose of experimental treatment. All adverse events of previous therapy must have resolved. Palliative radiation therapy to a limited field is allowed within this 3 week period.
4. Be willing and able to provide written informed consent/assent for the trial.
5. Be ≥ 18 years of age on day of signing informed consent.
6. Have measurable disease based on RECIST 1.1.
7. Have a performance status of 0-2 on the ECOG Performance Scale.
8. LVEF assessment with documented LVEF $\geq 50\%$ by either TTE or MUGA (TTE preferred test) within 6 months from first study drug administration
9. Demonstrate adequate organ function as defined in **Error! Reference source not found..** All screening labs should be performed within 10 days of treatment initiation.

Table 1. Adequate Organ Function Laboratory Values

System	Laboratory Value
Hematological	
Absolute neutrophil count (ANC)	$\geq 1,500$ /mcL
Platelets	$\geq 100,000$ / mcL
Hemoglobin	≥ 9 g/dL or ≥ 5.6 mmol/L (within 7 days of assessment)
Renal	
Serum creatinine OR Measured or calculated ^a creatinine clearance (GFR can also be used in place of creatinine or CrCl)	≤ 1.5 X upper limit of normal (ULN) OR ≥ 30 mL/min for subject with creatinine levels > 1.5 X institutional ULN
Hepatic	
Serum total bilirubin	≤ 1.5 X ULN OR Direct bilirubin \leq ULN for subjects with total bilirubin levels > 1.5 ULN
AST (SGOT) and ALT (SGPT)	≤ 2.5 X ULN OR ≤ 5 X ULN for subjects with liver metastases
Albumin	> 2.5 mg/dL
Coagulation	
International Normalized Ratio (INR) or Prothrombin Time (PT)	≤ 1.5 X ULN unless subject is receiving anticoagulant therapy as long as PT or PTT is within therapeutic range of intended use of anticoagulants
Activated Partial Thromboplastin Time (aPTT)	≤ 1.5 X ULN unless subject is receiving anticoagulant therapy

	as long as PT or PTT is within therapeutic range of intended use of anticoagulants
^a Creatinine clearance should be calculated per institutional standard.	

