7 TREATMENT DISCONTINUATION AND ADVERSE EVENT MANAGEMENT

Dose reductions or dose escalations are not permitted in this study. Dose delay criteria as noted below apply for all drug-related adverse events regardless of whether or not the event is attributed to nivolumab, relatlimab, or both. All study drugs must be delayed until treatment can resume. Reasons for permanent treatment discontinuation include the following:

- Any drug-related/immune-related Grade 4 toxicity, except for endocrinopathy and asymptomatic elevations of amylase and lipase.
- Any Grade 3 elevation of liver function tests or colitis not responding to steroids, infliximab and/or mycophenolate mofetil.
- Any other drug-related/immune-related Grade 3 toxicity, **EXCLUDING:**
 - *Grade 3 nausea/vomiting controlled by medical intervention within 72 hours*
 - *Grade 3 immune-related AEs (other than ocular events, colitis, myocarditis and pneumonitis) that improve to Grade \leq 1 or baseline within 14 days after the initiation of supportive care or corticosteroid therapy*
 - *Grade 3 endocrinopathy that is managed with or without systemic corticosteroid therapy and/or hormone replacement therapy and the subject is asymptomatic or minimally or transiently symptomatic based on Investigator assessment*
 - *Grade 3 fatigue lasting \leq 7 days from onset*
 - *Grade 3 rash in the absence of desquamation, with no mucosal involvement, that does not require systemic steroids, that does not interfere with activities of daily living and resolves to Grade 1 by the next dose of scheduled treatment or 14 days, whichever is longer*
 - *Any grade vitiligo or alopecia*
- Grade 2 or higher episcleritis, uveitis, or iritis
- Grade 2 pneumonitis that does not resolve to \leq Grade 1 within 3 days of initiation of maximal supportive treatment.

If treatment is withheld > 6 weeks from the last dose, the participant must be permanently discontinued from study therapy.

Table 3. Adverse Event Management Rules

Toxicity	Hold Treatment For Grade	Timing for Restarting Treatment	Treatment Discontinuation
Diarrhea/Colitis	2-3	Toxicity resolves to Grade 0-1	Toxicity does not resolve within 6 weeks of last dose or inability to reduce corticosteroid to 10 mg or less of prednisone or equivalent per day within 12 weeks
	4	Permanently discontinue	Permanently discontinue
AST, ALT, or Increased Bilirubin	2	Toxicity resolves to Grade 0-1	Toxicity does not resolve within 6 weeks of last dose

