	3-4	Permanently discontinue (see exception below) ^a	Permanently discontinue
Type 1 diabetes mellitus (if new onset) or Hyperglycemia	T1DM or 3-4	Hold therapy for new onset Type 1 diabetes mellitus or Grade 3-4 hyperglycemia associated with evidence of beta cell failure	Resume therapy when patients are clinically and metabolically stable
Hypophysitis	2-4	Toxicity resolves to Grade 0-1. Therapy can be continued while endocrine replacement therapy is instituted	Toxicity does not resolve within 6 weeks of last dose or inability to reduce corticosteroid to 10 mg or less of prednisone or equivalent per day within 6 weeks
Hyperthyroidism	3	Toxicity resolves to Grade 0-1	Toxicity does not resolve within 6 weeks of last dose or inability to reduce corticosteroid to 10 mg or less of prednisone or equivalent per day within 6 weeks
	4	Permanently discontinue	Permanently discontinue
Hypothyroidism		Therapy can be continued while thyroid replacement therapy is instituted	Therapy with can be continued while thyroid replacement therapy is instituted
Infusion Reaction	2 ^b	Toxicity resolves to Grade 0-1	Permanently discontinue if toxicity develops despite adequate premedication
	3-4	Permanently discontinue	Permanently discontinue
Pneumonitis	2	Toxicity resolves to Grade 0-1	Toxicity does not resolve within 6 weeks of last dose or inability to reduce corticosteroid to 10 mg or less of prednisone or equivalent per day within 6 weeks
	3-4	Permanently discontinue	Permanently discontinue
Renal Failure or Nephritis	2	Toxicity resolves to Grade 0-1	Toxicity does not resolve within 6 weeks of last dose or inability to reduce corticosteroid to 10 mg or less of prednisone or equivalent per day within 6 weeks
	3-4	Permanently discontinue	Permanently discontinue
All Other Drug-Related Toxicity ^c	3 or Severe	Toxicity resolves to Grade 0-1	Toxicity does not resolve within 6 weeks of last dose or inability to reduce corticosteroid to 10 mg or less of prednisone or equivalent per day within 6 weeks
	4	Permanently discontinue	Permanently discontinue

Note: Permanently discontinue for any severe or Grade 3 drug-related AE that recurs or any life-threatening event.

^a For patients with liver metastasis who begin treatment with Grade 2 AST or ALT, if AST or ALT increases by greater than or equal to 50% relative to baseline and lasts for at least 1 week then patients should be discontinued.

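### Patients with liver metastases may enter at Grade 2 AST/ALT, but the Table 3 Grade 2 row ignores baseline, and its link to footnote a and the section 7 Grade 3 liver bullet is unclear

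*Combined protocol and SAP*

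**What the plan says.** - **Entry (section 4.0, Table 1).** The AST and ALT limit is 2.5 x ULN in general, with an upper limit of "5 X ULN for subjects with liver metastases".
- **Grade 2 (section 7, Table 3, row "AST, ALT, or Increased Bilirubin").** Treatment is held. The restart condition is "Toxicity resolves to Grade 0-1". Treatment is discontinued if this has not happened within 6 weeks of the last dose. The row carries no footnote mark and does not mention baseline.
- **Grade 3-4 (same row group).** The restart cell reads "Permanently discontinue (see exception below" and carries the mark for footnote a. The discontinuation cell beside it orders permanent discontinuation and carries no mark.
- **Footnote a.** It begins "For patients with liver metastasis who begin treatment with Grade 2 AST or ALT" and calls for discontinuation when AST or ALT rises by at least 50% over baseline and the rise lasts at least 1 week. It gives no hold or restart rule for smaller or shorter rises.
- **Section 7 list of reasons for permanent discontinuation.** One bullet names Grade 3 liver test elevations and colitis together, followed by a qualifier about failure to respond to steroids, infliximab or mycophenolate. It is not clear whether the qualifier covers both conditions or only colitis. Elsewhere in the list, one sub-bullet on certain Grade 3 immune-related events accepts recovery to Grade 1 "or baseline within 14 days after the initiation of supportive care or corticosteroid therapy".
- **Scope.** Section 7 applies its delay criteria to drug-related events. Section 13.4.4 treats a condition present at screening as baseline, not as an adverse event, but records any later deterioration as one. Section 7 also sets a general 6-week limit on withholding.

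**The concern.** The protocol knowingly admits patients whose AST or ALT is already Grade 2, then manages Grade 2 on study as if everyone had started at Grade 0-1. For these patients the restart condition is a better grade than the one they were admitted with.

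The rule that does look at baseline sits on a different row, and it is not clear what that rule permits. A site facing a modest drug-related rise in such a patient cannot tell from the text whether the Grade 2 row, footnote a or the section 7 bullet governs. Two sites or two investigators could act differently on the same laboratory value. What is at stake is consistent safety management and avoidable loss of exposure in patients the trial chose to enrol. Section 1.7.3 says that metastases go mainly to the liver, so the provision for liver metastases is not a remote corner of the protocol.

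**Working it through.** The plan states no figure to reproduce here. The check sets the rules side by side and then applies them literally to example values.

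**Step 1: what triggers the Grade 2 row.** An unchanged Grade 2 entry value is not an adverse event (13.4.4), so it does not trigger a hold. A worsening within Grade 2 that is judged drug-related is an adverse event and does trigger the row.

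**Step 2: what the row then requires.** The patient must reach Grade 0-1, better than the Grade 2 entry value, within 6 weeks (42 days) of the last dose. If the rise is first found at the next scheduled Day 1, 28 days after the last dose, 42 - 28 = 14 days remain. With the visit window of 3 days either way, the range is 42 - 31 = 11 to 42 - 25 = 17 days. This step needs no numerical grade limit, because footnote a itself names Grade 2 at baseline.

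**Step 3: worked values.** Section 13 names CTCAE 5.0, but the documents do not give its AST/ALT limits. *Assumption:* grades are multiples of ULN, Grade 2 runs from L to 5 x ULN (L tried at 2.5 and 3), and Grade 3 starts above 5 x ULN. Take a baseline of 4.0 x ULN:

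| On-study value (x ULN) | Rise over baseline | Assumed grade | Table 3, read literally |
|---|---|---|---|
| 4.8 | 4.8/4.0 - 1 = 20% | 2 | Hold; restart at Grade 0-1; discontinue if not there by 6 weeks from last dose |
| 5.5 | 5.5/4.0 - 1 = 37.5% | 3 | Footnote a stop criterion not met |
| 6.0 | 6.0/4.0 - 1 = 50% | 3 | Footnote a stop criterion met if it lasts at least 1 week |

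To restart after 4.8, the value must fall to L or below. That is 1 - 3/4 = 25% under the patient's own baseline with L = 3, or 1 - 2.5/4 = 37.5% under it with L = 2.5.

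**Step 4: where a larger rise could be spared.** A Grade 3 value v with a rise below 50% over baseline b needs 5 < v < 1.5b, so b > 5/1.5 = 3.33 x ULN. At or below 3.33, every Grade 3 value is already a rise of at least 50%, and a sustained rise shows no inversion. For example, 1.5 x 3.2 = 4.8 x ULN, so from a baseline of 3.2 the 50% threshold is reached while the value is still Grade 2, on a row that does not carry the footnote mark.

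**Step 5: the possible readings.**

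| Reading of footnote a | Reading of the section 7 bullet | Result |
|---|---|---|
| Spares Grade 3 rises below 50% | Stops only non-responding elevations | A sustained smaller rise can end treatment while a larger one does not (baselines above about 3.33 x ULN) |
| Spares Grade 3 rises below 50% | Stops every Grade 3 elevation | Section 7 contradicts footnote a |
| Spares nothing; the unmarked discontinuation cell governs | Stops every Grade 3 elevation | No inversion, but the stated exception excepts nothing |
| Spares nothing; the unmarked discontinuation cell governs | Stops only non-responding elevations | Table 3 contradicts the section 7 bullet |
| Governs every patient who starts at Grade 2, whatever the row | Either | Conflicts with the unmarked Grade 2 row, and still has no hold or restart rule |

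With grading by multiples of ULN, no combination gives one complete and consistent rule.

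**The case against.** The strongest case against is that the inversion is not established. Footnote a says only when to discontinue; it never says that a Grade 3 rise below 50% may continue. The discontinuation cell of that row is unmarked, and the section 7 bullet may stop every Grade 3 liver elevation. If on-study grade were set relative to an abnormal baseline, the problem could disappear. The footnote's words cover any patient who starts at Grade 2, so this may be a misplaced mark.

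Most of that stands. It limits the inversion to one reading, but leaves the need to reconcile: each alternative in the table above is itself a conflict or an exception without effect, and the documents do not say that grading is relative to baseline.

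A reader might also infer the following, which the documents do not support:

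- *That the protocol definitely treats larger rises more leniently.* This needs a particular reading of both footnote a and the section 7 bullet, plus grade limits that the documents do not give.
- *That entering at Grade 2 is enough to trigger a hold, or that a small rise ends treatment at once.* The first is excluded by 13.4.4. In the second case, treatment ends only through failure to reach Grade 0-1 in time.
- *That section 7 generally accepts a return to baseline.* One sub-bullet does, for Grade 3 immune-related events in a category separate from the liver bullet.
- *That bilirubin shows the same inversion.* Table 1 also has an alternative entry route "for subjects with total bilirubin levels > 1.5 ULN", but footnote a does not cover bilirubin, so no inversion can arise there.
- *That ORR or the stage 1 decision is measurably at risk.* The share entering at Grade 2 is not given. Those affected would also need a drug-related rise, failure to recover in time, and a response lost through stopping. Section 6.1 keeps patients who stop treatment on study.

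**Conclusion.** The concern holds as an unreconciled set of hold, restart and discontinuation rules for patients admitted with Grade 2 AST/ALT. The firm part rests on the text, with grade read the same way at entry and on study: after a drug-related worsening within Grade 2, such a patient must recover to better than the entry grade within 6 weeks of the last dose or stop, and no baseline provision is marked on that row.

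The inversion is conditional. It requires that footnote a spares Grade 3 rises below 50%, that the section 7 bullet does not stop them, that grades are multiples of ULN with Grade 2 ending at 5 x ULN, and that baseline lies above about 3.33 and below 5 x ULN.

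The number of patients affected, and any effect on response rates, cannot be estimated from the documents. The point should be corrected because it concerns when treatment stops in patients the protocol expects to enrol. It does not call the two-stage design into question.

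**What to change.** Reconcile Table 1, the Grade 2 and Grade 3-4 AST/ALT rows of Table 3, footnote a and the section 7 bullet on Grade 3 liver tests, so that a patient admitted with Grade 2 AST/ALT falls under one consistent hold, restart and discontinuation rule. In doing so, state:

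1. which rows and cells footnote a governs, and what applies to rises that do not meet its criterion;
2. whether the non-response qualifier in the section 7 bullet covers liver tests or only colitis;
3. whether on-study grade is absolute or relative to baseline when the entry value is abnormal.

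The sponsor decides the clinical rule; none is proposed here. The cost is a wording amendment. No tests are added, since sections 10.2 and 10.3 already schedule a comprehensive metabolic panel at every cycle.

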8 NIVOLUMAB

8.1 Description of Investigational Product

Nivolumab is a soluble protein consisting of 4 polypeptide chains, which include 2 identical heavy chains and 2 identical light chains. Nivolumab is produced from cell culture using a Chinese Hamster Ovary (CHO) cell line. The physical and chemical properties of nivolumab drug substance are provided in Table 3.1-1 of the Investigator's Brochure.

8.2 Mechanism of Action

Binding of the PD-1 ligands, PD-L1 and PD-L2, to the PD-1 receptor found on T cells, inhibits T- cell proliferation and cytokine production. Upregulation of PD-1 ligands occurs in some tumors and signaling through this pathway can contribute to inhibition of active T-cell immune surveillance of tumors. Nivolumab is a human immunoglobulin G4 (IgG4) monoclonal antibody that binds to the PD-1 receptor and blocks its interaction with PD-L1 and PD-L2, releasing PD-1 pathway-mediated inhibition of the immune response, including the anti-tumor immune response. In syngeneic mouse tumor models, blocking PD-1 activity resulted in decreased tumor growth.

Combined nivolumab (anti-PD-1) and ipilimumab (anti-CTLA-4) mediated inhibition results in enhanced T-cell function that is greater than the effects of either antibody alone, and results in improved anti-tumor responses in metastatic melanoma and advanced RCC. In murine syngeneic tumor models, dual blockade of PD-1 and CTLA-4 resulted in increased anti-tumor activity.

8.3 Dosage Form, Agent Preparation, Handling & Storage Guidelines

8.3.1 Dosage Form

The nivolumab (Opdivo™) dosage forms are provided in [Table 3.2.1-1 of the Investigator's Brochure](#). The drug products are sterile, non-pyrogenic, single-use, isotonic aqueous solutions for intravenous (IV) infusion. Nivolumab Injection, 40 mg/Vial (10 mg/mL), 100 mg/Vial (10 mg/mL), and 240 mg/Vial (10 mg/mL) are also referred to as nivolumab injection.

8.3.2 Acquisition and Accountability

The Investigator or designee is responsible for maintaining accurate dispensing records of the study treatment throughout the clinical study. The study treatment accountability log includes information including a patient identifier, amount and date dispensed, and amount and date returned to the pharmacy, if applicable. Product returned to the research pharmacy will be stored under the same conditions as products not yet dispensed but will be marked as 'returned' and kept separate from the products not yet dispensed. All dispensing and accountability records should be stored as per IND regulations. The pharmacist will dispense study treatment for each participant according to the pharmacy reference manual.

8.3.3 Preparation and Administration

Nivolumab injection is to be administered as an IV infusion through a 0.2-micron to 1.2-micron pore size, low-protein binding (polyethersulfone membrane) in-line filter at the protocol-specified doses and infusion times. It is not to be administered as an IV push or bolus injection. When the dose is based on patient weight (ie, mg/kg), nivolumab injection can be infused undiluted (10 mg/mL) or diluted with 0.9% sodium chloride injection or 5% dextrose injection to protein concentrations as low as 0.35 mg/mL. When the dose is fixed (eg, 240 mg, 360 mg, or 480 mg flat dose), nivolumab injection can be infused undiluted or diluted so as not to exceed a total infusion volume of 160 mL. For patients weighing less than 40 kilograms (kg), the total volume of infusion must not exceed 4 mL per kg of patient weight.

During drug product preparation and handling, vigorous mixing or shaking is to be avoided. Instructions for dilution and infusion of nivolumab injection will be provided to the clinical site. Care must be taken to ensure sterility of the prepared solution as the product does not contain any antimicrobial preservative or bacteriostatic agent. Nivolumab infusions are compatible with polyvinyl chloride (PVC) or polyolefin containers and infusion sets, and glass bottles.

8.3.4 Packaging, Labeling, and Storage

Upon supply to site, study drugs will be labeled “for investigational use only” as per FDA regulations.

Nivolumab Injection

Vials of nivolumab injection must be stored at 2°C to 8°C (36°F to 46°F) and protected from light and freezing. The unopened vials can be stored at room temperature (up to 25°C, 77°F) and room light for up to 48 hours.

Undiluted Nivolumab Injection and Diluted Nivolumab Injection in the IV Container

The administration of nivolumab infusion must be completed within 24 hours of preparation. If not used immediately, the infusion solution may be stored under refrigeration conditions (2°C to 8°C, 36°F to 46°F) for up to 24 hours, and a maximum of 8 hours of the total 24 hours can be at room temperature (up to 25°C, 77°F) and room light. The maximum of 8 hours under room temperature and room light conditions includes the product administration period.

8.4 Disposal and Destruction

All unused and/or partially used Investigational Medicinal Product will be destroyed on site as per Institutional SOP and the destruction documented. Copy of the drug destruction document will be provided to BMS. IMP handling document will be provided at the time of Study activation.

9 RELATLIMAB

9.0 Description of Investigational Product

Relatlimab, also referred to as BMS-986016-01, BMS-986016, or anti-LAG-3, was selected for dosage form development. Relatlimab is a soluble protein consisting of 4 polypeptide chains that include 2 identical heavy chains and 2 identical light chains and is a human IgG4 monoclonal antibody directed against human LAG-3. Relatlimab is produced from cell culture using a Chinese hamster ovary (CHO) cell line. The physical and chemical properties of relatlimab drug substance are summarized in Table 3.1-1 of the Investigator's Brochure.

9.1 Mechanism of Action

Upon administration, relatlimab binds to LAG-3 on tumor infiltrating lymphocytes (TILs). This may activate antigen-specific T lymphocytes and enhance cytotoxic T cell-mediated tumor cell lysis, which leads to a reduction in tumor growth. LAG-3 is a member of the immunoglobulin superfamily (IgSF) and binds to major histocompatibility complex (MHC) class II. LAG-3 expression on TILs is associated with tumor-mediated immune suppression.²⁴

9.2 Dosage Form, Agent Preparation, Handling & Storage Guidelines

9.2.1 Dosage Form

Relatlimab will be given as an intravenous (IV) infusion. There are three drug products available for intravenous (IV) administration; information relating to the drug products are provided in [Table 3.2.1-1 of the Investigator's Brochure](#). The drug products are sterile, non-pyrogenic, single-use, isotonic aqueous solutions.

9.2.2 Acquisition and Accountability

The Investigator or designee is responsible for maintaining accurate dispensing records of the study treatment throughout the clinical study. The study treatment accountability log includes information including a patient identifier, amount and date dispensed, and amount and date returned to the pharmacy, if applicable. Product returned to the research pharmacy will be stored under the same conditions as products not yet dispensed but will be marked as 'returned' and kept separate from the products not yet dispensed. All dispensing and accountability records should be stored as per IND regulations. The pharmacist will dispense study treatment for each participant according to the pharmacy reference manual.

